## Discontinuation/withdrawal of participants from the study:

Each participant has the right to withdraw from the study at any time. In addition, the investigator may discontinue a participant from the study at any time if the investigator considers it necessary for any reason including:

- Pregnancy
- Ineligibility (either arising during the study or retrospective having been overlooked at screening)
- Significant protocol deviation
- An adverse event which requires discontinuation of the use of the study device or results in an inability to continue to comply with study procedures (e.g. severe skin irritation)
- Consent withdrawn

Reasons for withdrawal will be recorded. Some data may be excluded from participants who withdraw from the study, at the discretion of the PI and sponsor. If the participant is withdrawn due to an adverse event, the investigator will arrange for follow-up visits or telephone calls until the adverse event has been resolved.

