#### Sample Size Justification:

Based on preliminary tests using publicly available databases and internally collected data, the root mean squared error on respiration rate for our system ranges between 0.5 and 0.8 bpm. For an average respiration rate of 20bpm, this is equivalent to 2.5 to 4% error. We expect the relative error of the tidal volume performance to be similar. For these purposes, we will use a worst-case scenario of a standard deviation of 10%. Using the paired-difference equivalence test power formula, we calculate the number of subjects n needed to demonstrate that the 2 device measurements are equivalent ( $\delta = 0$ ) within 10% (B = 0.10). To obtain a 2-sided alternative with 90% power we set  $z\alpha = 1.96$ , and  $z\beta = 1.65$ . We can then calculate the required n = 13. This suggests that with 13 subjects we would be able to demonstrate equivalence (with 90% power) if the differences in the measurements between the CPM Device and the reference spirometers are within 10%. However, to better reflect a broader patient population and since we might be under-estimating our error, we plan to enroll 20 subjects.

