## **Endpoints**:

- Respiration Rate RMSE < 2 BPM between reference and test device at 8-40 BPM
- Relative Tidal Volume Precision has an  $R^2$  value > 0.5

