# Endpoints

Thoracic Impedance Precision (primary)

- Std < 6 Ohms from measurement to measurement (short term) within a subject
- Std of Z to reference  $X \le 6$  Ohms for short- and long-term measurements
- Respiration Rate Accuracy (secondary)
- RMSE < 2 bpm between reference and test device
- *Tidal Volume Accuracy (secondary)* 
  - $R^2$  value > 0.5

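### The protocol lets the investigator and sponsor drop data from withdrawn participants at their discretion, with no criterion, timing or reporting rule, so result-dependent exclusion is possible and could change an endpoint result

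*Combined protocol and SAP*

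**What the plan says.** The section on discontinuation and withdrawal of participants states: "Some data may be excluded from participants who withdraw from the study, at the discretion of the PI and sponsor". No condition is attached.

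The same section says that "the investigator may discontinue a participant from the study at any time if the investigator considers it necessary for any reason including" a list that covers significant protocol deviation, ineligibility discovered only in retrospect, and adverse events such as severe skin irritation. Reasons for withdrawal are to be recorded, and the Demographics paragraphs of both data analysis plans tabulate them.

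The results are judged against fixed limits. The healthy-cohort endpoint is "Respiration Rate RMSE < 2 BPM between reference and test device at 8-40 BPM". The pathologic cohort has "RMSE < 2 bpm between reference and test device" as a secondary endpoint, and 6 Ω limits on the impedance standard deviations as primary. No confidence bound is stated for any of them.

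The Effectiveness and Endpoint Analyses sections define no analysis set, no handling of incomplete records and no sensitivity analysis. All enrolled subjects are named only as the population for the demographic summaries.

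**The concern.** This is an explicit permission, and no other section limits it. The sponsor supplies the test device, has access to the data, and will use the study to support a 510(k) submission. No masking of test or reference readings is described. An exclusion decision could therefore be taken by people who know how the readings compare, and no reader of the report could tell.

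Participants enter the affected group partly through study-team decisions. Retrospective ineligibility matters most here. The healthy cohort attends one visit of about two hours, so a participant found ineligible afterwards may already have a complete record.

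RMSE gives heavy weight to the worst errors, and the limits are applied to 20 subjects per cohort. Removing a poorly measured subject always moves RMSE towards a pass. What is at stake is the credibility of a pass, and under some conditions the pass itself.

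**Working it through.** **Inputs from the documents.** 20 subjects per cohort. RMSE limit 2 bpm. Expected RMSE from the healthy-cohort Sample Size Justification: "the root mean squared error on respiration rate for our system ranges between 0.5 and 0.8 bpm". Impedance limit 6 Ω. Preliminary within-subject impedance SD of at most 5.1 Ω (pathologic-cohort Sample Size Justification).

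**Assumptions.** The documents give no withdrawal rate, no error figure for withdrawn subjects, and no pooling rule for RMSE. I assume equal weight per subject, which for full records equals pooling over readings, and I vary the rest.

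**1. The plan's own figures.** n = (zα + zβ)² × (SD/B)².
- Healthy: (1.96 + 1.65)² × (0.10/0.10)² = 13.03, against 13 stated.
- Pathologic: 13.03 × (5.1/6)² = 9.42, rounded up to the stated 10.

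Both reproduce within rounding. With a true difference of zero, zβ = 1.65 is consistent with 90% power. These calculations concern a mean difference and say nothing about which subjects count.

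**2. RMSE, full records.** Let b be the RMSE of the retained subjects and k the number excluded. The pooled value with everyone included reaches 2 bpm when each excluded subject has

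x = √[(20 × 2² − (20 − k) × b²) / k].

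For k = 1 and b = 0.8: √(80 − 19 × 0.64) = √67.84 = 8.24.

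| RMSE of the others (bpm) | One excluded | Two, each | Three, each |
|---|---|---|---|
| 0.5 (protocol) | 8.67 | 6.14 | 5.02 |
| 0.8 (protocol) | 8.24 | 5.85 | 4.80 |
| 1.8 (assumption) | 4.29 | 3.29 | 2.88 |
| 1.9 (assumption) | 3.38 | 2.74 | 2.49 |

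**3. RMSE, partial records.** The healthy-cohort table has 11 paced items within 8-40 BPM (items 3 to 13). If readings are pooled and the excluded subject completed m of the 11, then

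x = √[(4 × (209 + m) − 209 × b²) / m], where 209 = 19 × 11.

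- b = 0.8, m = 6: √(726.24/6) = 11.0 bpm.
- b = 0.8, m = 3: √(714.24/3) = 15.4 bpm.
- b = 1.8, m = 6: √(182.84/6) = 5.52 bpm.

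**4. A middling case.** With the other 19 at 0.8, one full-record subject at 7 bpm gives √[(19 × 0.64 + 49)/20] = 1.75, which still passes with that subject included. With the others at 1.5 (assumption), the same subject gives √[(19 × 2.25 + 49)/20] = 2.14, a fail that becomes 1.50 on removal.

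**5. Is 8.24 reachable?** Suppose, as pure assumption, that one subject's 30, 35 and 40 BPM items are read at half rate (errors 15, 17.5 and 20) and the other eight items have error 0.8. That subject's RMSE is √[(225 + 306.25 + 400 + 8 × 0.64)/11] = 9.2. The pooled value is then 2.2 with the subject and 0.8 without.

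**6. Impedance.** Put the other 19 at 5.1 Ω, the upper preliminary figure.
- Root-mean-square pooling (assumption): √(20 × 36 − 19 × 26.01) = √225.81 = 15.0 Ω.
- Simple average of within-subject SDs, as listed in Outcome Measures: 20 × 6 − 19 × 5.1 = 23.1 Ω.

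**The case against.** The strongest reply is that the effect is small on the plan's own figures. At 0.8 bpm, one full-record subject would need about ten times the expected error before removal mattered, and someone who leaves early carries less weight still. That stands as a limit on size. It does not cover retrospective discontinuation of a complete record, and the plan itself allows that its error may be under-estimated.

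A second reply is that poor readings are dealt with earlier. Study Procedures require a repeat when contact or tilt errors cannot be resolved, or when the device peels and the data look questionable. The analytics engine adds a 30-second quality check. This should remove many bad readings before anyone withdraws, but none of it restricts what may be excluded afterwards. It also means that data quality does not depend on this discretion.

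A third reply is that the rule is narrow: it touches only withdrawals, from visits completed within one day, and reasons are tabulated. That is fair, though the tabulation would not show which data were dropped.

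Three stronger readings are tempting, and the documents support none of them:
- A reader might infer that dropping one poor subject would turn a failed RMSE endpoint into a pass. That needs a very large error in that subject, or other subjects already close to 2 bpm, and the documents establish neither.
- A reader might infer that the sponsor decides with both devices' readings in hand. The text is silent on timing; it neither says so nor prevents it.
- A reader might infer that withdrawals for skin problems or deviations go with poor contact and poor readings. No section says so.

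**Conclusion.** The point holds as a defect in a stated rule: data from withdrawn participants may be excluded without criterion, timing or disclosure, and no endpoint analysis set overrides this. Result-dependent exclusion is therefore possible and could change an endpoint result.

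How much it could matter is conditional. Within the protocol's expected 0.5 to 0.8 bpm, one excluded full-record subject would need an RMSE of about 8.2 to 8.7 bpm, and a partial record would need more. The threshold falls to about 4.3 bpm only if the others are near 1.8 bpm, which is an assumption. The impedance thresholds, about 15 or 23 Ω, put all other subjects at the upper preliminary SD. All these figures rest on equal weighting or the stated pooling. They show what would be required and say nothing about how likely it is.

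Confidence is high about the wording and low about any particular effect on the result. The change should be made, because the credibility problem does not depend on a flip occurring.

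**What to change.** Replace the exclusion sentence with:

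> All paired readings that meet the protocol's measurement-completion and QC rules and were collected before withdrawal are included in the primary analysis, unless the participant withdraws consent for use of the data. Any other exclusion must follow a criterion fixed before CPM and reference results are compared. Every exclusion is listed with its reason, and endpoint results are reported with and without the excluded data.

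Tying inclusion to the completion and QC rules already in the protocol avoids an undefined notion of a valid reading.

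The cost is one protocol sentence replaced by a short paragraph, one listing and one sensitivity analysis. The sponsor gives up its discretion. No procedure, visit or sample size changes.

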## Malfunctioning or Broken Investigational Devices:

In the case that the study device malfunctions or breaks for any reason before the completion of the baseline, a new device will be fitted and assigned to the participant, the old device will be replaced by this one, and the full procedure will be followed as written. In the case that a CPM device malfunctions or breaks for any reason after the baseline measurement has been taken, the procedure below will be followed:

1) Markings are made using skin-compatible marker to relocate a new device after the malfunctioning one is removed;

- 2) Malfunctioning device is removed from the skin;
- 3) New device is fitted, placed according to markings, and a new baseline reading is taken (a new patient ID will be assigned in the app);
- 4) Protocol continues as normal, starting from the dataset on which the device malfunctioned;
- 5) A note is made in the CRF of:
  - a. the exact nature of device malfunction;
  - b. the time that the device was replaced;
  - c. the measurement on which the device malfunctioned (e.g. metered breathing at 30BPM);
  - d. and the new device ID and patient ID.

# **Resources:** Describe the available resources to conduct the research (personnel, time, facilities, mentor commitment, etc.):

This research study will be conducted in [name] laboratory in the Joseph building at St Mary's hospital. The laboratory is equipped with all necessary equipment to perform human physiology experiments in a safe and secure environment. The study team has a long history of conducting Mayo IRB approved research protocols involving controlled breathing exercises in healthy participants. All personnel involved with this study have completed human subject protection certification such as CITI training. The combined expertise of the study team and the Sponsor will ensure that this research project is conducted safely and completed in a timely manner. This study has no financial implications for Mayo Clinic other than person-hours required to recruit patients and run the study. All materials related to the CPM System (under test) used in the study will be provided by Analog Devices, and the reference devices and materials (SpO2 monitor, spirometry device, metabolic cart, bioimpedance devices) will be supplied by [name] lab.

(1a) This is a multisite study involving Mayo Clinic and non Mayo Clinic sites. *When checked, describe in detail the research procedures or activities that will be conducted by Mayo Clinic study staff.* 

(1b) Mayo Clinic study staff will be engaged in research activity at a non Mayo Clinic site. *When checked, provide a detailed description of the activity that will be conducted by Mayo Clinic study staff.* 

#### **Subject Information**

Target accrual is the proposed total number of subjects to be included in this study at Mayo Clinic. A "Subject" may include medical records, images, or specimens generated at Mayo Clinic and/or received from external sources.

## Target accrual:

20 healthy and 20 pathologic adult volunteers will be recruited for this study (a total of 40). More subjects than this will likely have to be approached for potential participation.

## Subject population (children, adults, groups):

Healthy Cohort

The subject population will include healthy adult volunteers (over the age of 18).

## Pathologic Cohort

The subject population will include those diagnosed with cardiopulmonary conditions who are over the age of 21. This can include those who are taking diuretic medications, living with heart failure, Chronic Obstructive Pulmonary Disorder (COPD), or recovering from coronary-artery disease related events.

# **Inclusion Criteria:**

Healthy Cohort

- Adults over the age of 18 and who are willing and able to give informed consent
- Willing to participate in all activities related to this study, including trimming chest hair and wearing a reference device and the CPM wearable device
- Volunteers of any race, any gender
- Range of physiques
- Healthy

## Pathologic Cohort

- Adults over the age of 21 and who are willing and able to give informed consent
- Willing to participate in all activities related to this study, including wearing a capnography device, thoracic impedance reference device, and the CPM wearable device
- Those who:
  - Are taking diuretic medication
  - o Are living with heart failure
  - Have chronic obstructive pulmonary disorder (COPD)
  - Are recovering from a coronary-artery disease related event.
- Volunteers of any race, any gender
- Range of physiques

## **Exclusion Criteria:**

Healthy Cohort

- Injury or skin disturbance in the area of the test device
- Pregnant
- Currently smokes cigarettes
- Has known respiratory conditions such as:
  - o Flu
  - Pneumonia/bronchitis
  - o Shortness of breath/respiratory distress
  - Respiratory or lung surgery
  - Emphysema, COPD, lung disease
- Has self-reported heart or cardiovascular conditions such as chest pain, AFib, CHF, cardiomyopathy, or other conditions that could interfere with cardiopulmonary function
- Has other self-reported health conditions that could interfere with the breathing patterns and exercises detailed in the protocol (including wearing a capnography mask)

#### Pathologic Cohort

- Under the age of 21
- Cognitive or physical impairment sufficient enough to interfere with informed consent or successful completion of the protocol
- Injury or skin disturbance in the area of the test device
- Pregnant
- Have life-threatening arrhythmias which require hospital admission and constant monitoring
- Has other self-reported health conditions that could interfere with wearing a capnography mask

#### **Research Activity**

Check all that apply and complete the appropriate sections as instructed.

- 1. Drug & Device: Drugs for which an investigational new drug application is not required. Device for which (i) an investigational device exemption application is not required; or the medical device is cleared/approved for marketing and being used in accordance with its cleared/approved labeling. (Specify in the Methods section)
- 2. Blood: Collection of blood samples by finger stick, heel stick, ear stick, or venipuncture.
- 3. Biological specimens other than blood: Prospective collection of human biological specimens by noninvasive means that may include: urine, sweat, saliva, buccal scraping, oral/anal/vaginal swab, sputum, hair and nail clippings, etc.
- 4. X Tests & Procedures: Collection of data through noninvasive tests and procedures routinely employed in clinical practice that may include: MRI, surface EEG, echo, ultrasound, moderate exercise, muscular strength & flexibility testing, biometrics, cognition testing, eye exam, etc. (Specify in the Methods section)
- 5. Data (medical record, images, or specimens): Research involving use of existing and/or prospectively collected data.
- 6. Digital Record: Collection of electronic data from voice, video, digital, or image recording. (Specify in the Methods section)
- 7. Survey, Interview, Focus Group: Research on individual or group characteristics or behavior, survey, interview, oral history, focus group, program evaluation, etc. (Specify in the Methods section)

NIH has issued a *Certificate of Confidentiality* (COC). When checked, provide the institution and investigator named on the COC and explain why one was requested.

#### **Biospecimens** – Categories 2 and 3

(2) Collection of blood samples. When multiple groups are involved copy and paste the appropriate section below for example repeat section b when drawing blood from children and adults with cancer.

a. From healthy, non-pregnant, adult subjects who weigh at least 110 pounds. For a minimal risk application, the amount of blood drawn from these subjects may not exceed 550ml in an 8 week period and collection may not occur more frequently than 2 times per week.

Volume per blood draw: \_\_\_\_ml

Frequency of blood draw (e.g. single draw, time(s) per week, per year, etc.)

b. From other adults and children considering age, weight, and health of subject. For a minimal risk application, the amount of blood drawn from these subjects may not exceed the lesser of 50 ml or 3 ml per kg in an 8 week period, and collection may not occur more frequently than 2 times per week. Volume per blood draw: \_\_\_\_\_ml Frequency of blood draw (e.g. single draw, time(s) per week, per year, etc.)

(3) Prospective collection of biological specimens other than blood:

## Review of medical records, images, specimens – Category 5

For review of existing data: provide a date range or an end date for when the data was generated. The end date can be the date this application was submitted to the IRB. Example: 01/01/1999 to 12/31/2015 or all records through mm/dd/yyyy.

#### **Date Range:**

Check all that apply (data includes medical records, images, specimens).

(5a) Only data that exists before the IRB submission date will be collected.

(5b) The study involves data that exist at the time of IRB submission **and** data that will be generated after IRB submission. Include this activity in the Methods section. Examples

- The study plans to conduct a retrospective chart review and ask subjects to complete a questionnaire.
- The study plans to include subjects previously diagnosed with a specific disease and add newly diagnosed subjects in the future.

(5c) The study will use data that have been collected under another IRB protocol. Include in the Methods section and enter the IRB number from which the research material will be obtained. *When appropriate, note* when subjects have provided consent for future use of their data and/or specimens as described in this protocol.

Enter one IRB number per line, add more lines as needed

🗌 Data	Specimens Data & Specimens	
🗌 Data	Specimens Data & Specimens	
🗌 Data	Specimens Data & Specimens	

☐ (5d) This study will obtain data generated from other sources. Examples may include receiving data from participating sites or an external collaborator, accessing an external database or registry, etc. Explain the source and how the data will be used in the Methods section.

(6) Video audio recording: *Describe the plan to maintain subject privacy and data confidentiality, transcription, store or destroy, etc.* 

#### HIPAA Identifiers and Protected Health Information (PHI)

Protected health information is medical data that can be linked to the subject directly or through a combination of indirect identifiers.

Recording identifiers (including a code) during the conduct of the study allows you to return to the medical record or data source to delete duplicate subjects, check a missing or questionable entry, add new data points, etc. De-identified data is medical information that has been stripped of all HIPAA identifiers so that it cannot be linked back to the subject. De-identified data is **rarely** used in the conduct of a research study involving a chart review.

Review the list of subject identifiers below and, if applicable, check the box next to each HIPAA identifier being recorded at the time of data collection or abstraction. Identifiers apply to any subject enrolled in the study including Mayo Clinic staff, patients and their relatives and household members.

**Internal** refers to the subject's identifier that will be recorded at Mayo Clinic by the study staff. **External** refers to the subject's identifier that will be shared outside of Mayo Clinic.

Check all that apply:	INTERNAL	EXTERNAL
Name		
Mayo Clinic medical record or patient registration number, lab accession,		
specimen or radiologic image number		
Subject ID, subject code or any other person-specific unique identifying		
number, characteristic or code that can link the subject to their medical data		
Dates: All elements of dates [month, day, and year] directly related to an		
individual, their birth date, date of death, date of diagnosis, etc.		
Note: Recording a year only is not a unique identifier.		
Social Security number		
Medical device identifiers and serial numbers	Х	Х
Biometric identifiers, including finger and voice prints, full face photographic		
images and any comparable images		
Web Universal Resource Locators (URLs), Internet Protocol (IP) address		
numbers, email address		
Street address, city, county, precinct, zip code, and their equivalent geocodes		
Phone or fax numbers		
Account, member, certificate or professional license numbers, health		
beneficiary numbers		
Vehicle identifiers and serial numbers, including license plate numbers		
Check 'None' when none of the identifiers listed above will be recorded,	None	None None
maintained, or shared during the conduct of this study. (exempt category 4)		

Data Analysis

Power analyses may not be appropriate if this is a feasibility or pilot study, but end-point analysis plans are always appropriate even if only exploratory. Provide all information requested below, or provide justification if not including all of the information.

